18.1.2 Analyses

Population: FAS and PP

Stratification: Table: Add the strata as needed in case subjects with dose modification exceeding 20% based on enrolled population as per section 7.3:

- a. Subjects on 1.5 mg only
- b. Subjects on 0.75 mg only
- c. Subjects with any dose modification*

* Subjects who have received at least one dose of 1.5 mg and at least one dose of 0.75 mg

Listing: by subject and events

Statistics: The incidence of AEs (including deaths, SAEs, TEAEs, hypoglycemia, including severe hypoglycemia and GI disorders) will be summarised as frequency and percentages.

The listings will be presented for the hypoglycaemia events.

The incidence of AE (death, SAE, and TEAE) will be summarized. The rate per year (i.e., number of deaths, SAE, and TEAEs per subject per year over the study period) will be assessed using a negative binomial model with the log of the study treatment exposure time as an offset variable and the model will be performed as per details mentioned below.

The incidence of hypoglycemic AEs will be summarized. The number of hypoglycemic events per subject over the study period will be analysed as continuous variables and will be summarized as (n, mean, standard deviation, standard error, median, minimum, maximum).

The rate per year of hypoglycemic events, that is, the number of hypoglycemic events per patient-year (365.25 days) will be assessed using a negative binomial model, with baseline HbA1c and baseline insulin usage as covariates and the log of the study treatment exposure time as an offset variable.

The Negative Binomial Model i.e., the generalized linear model will be used with baseline HbA1c and baseline insulin usage and the log of the study treatment exposure time as offset variable.

The incidence rate, least square mean and corresponding 95% confidence interval will be provided for table.

Also, in case we have more than 20% data missing in any of the covariate, we will repeat the analysis after omitting the impacted covariate.

In case of multiple doses of insulin uptake per day, a sum of insulin per day will be used as the baseline insulin covariate. Regimen for subjects with more than 1 regimen type per day will be reviewed by

medical team. Insulin Dose level for subjects not on insulin will be considered as 0 and the corresponding regimen as 'Non'.

In case convergence is not met with the above variables, only baseline HbA1c and baseline insulin usage(Yes/No) will be considered.

Exposure-adjusted AE incidence will be presented by the severity and preferred term for the primary analysis.

Additionally, all the analysis will be repeated for the below mentioned subgroups:

- age (<65 year and \geq 65 year)
- HbA1c (<8.5 and \geq 8.5)
- Sex (Female and male)
- BMI category (<27 kg/m²) and \geq 27 kg/m²)

18.2 Proportion of patients reporting AEs and SAEs between baseline and Week 24

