9.3. Analyses Sets

For purposes of analysis, the following populations are defined:

Participant Analysis Set	Description
Enrolled	
 All participants who sign informed consent form and are screen positive
FAS	
 All patients who received at least 1 dose of study treatment and have at least 1 measurement of HbA1c after study treatment
Per-protocol set	
All patients in the FAS who meet the following criteria
 
 have no important protocol deviations that could impact the assessment of the primary objective (see SAP) are at least 80% compliant with the study drug in terms of dose taken have no instance of deviation from persistence with study drug in terms of no more than the 15 days gap between 2 consecutive doses complete the treatment phase (24 weeks) for the primary endpoint
Safety analysis set	
 All patients who received at least 1 dose of study treatment

Abbreviations: FAS = full analysis set; HbA1c = hemoglobin A1c; SAP = statistical analysis plan.

The FAS is used to analyze endpoints related to the efficacy objectives, and the safety analysis set is used to analyze the endpoints and assessments related to safety.

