9.4. Statistical Analyses

9.4.1. General Considerations

Statistical analysis of this study will be the responsibility of Lilly or its designee. Any change to the data analysis methods described in the protocol will require an amendment only if it changes a principal feature of the protocol. Any other change to the data analysis methods described in the protocol and the justification for making the change will be described in the CSR. Additional exploratory analyses of the data will be conducted as deemed appropriate.

All data will be entered, verified, and archived by a CRO external to Lilly and/or at Lilly. Data listings, summaries, and analyses will be performed by a CRO under the guidance and approval of statisticians at Lilly.

Summary statistics will be provided for the observed value, and change from baseline will be summarized.

Unless otherwise specified, listings will include all enrolled patients. Efficacy analyses will be conducted using the FAS.

Similarly, the exploratory measures (change in body weight from baseline and change in FBG from baseline) will be evaluated in the FAS population.

Also, safety analyses will be conducted on the safety population. The exploratory measures of vital signs (change in SBP, DBP, and pulse rate from baseline) will be analyzed using the safety population).

Unless otherwise specified, testing effect of dulaglutide on change from baseline will be conducted at a 2-sided alpha level of 0.05, and CIs will be calculated at 95%, 2-sided.

For continuous measures, summary statistics will include number of patients, mean, SD, median, minimum, maximum, and interquartile ranges for both the actual and the change from baseline measurements. Number of missing values will be specified along with this information.

For categorical measures, summary statistics will include sample size, frequency, and percentages. Number of missing values will be specified along with this information.

No multiplicity adjustment will be done in this study.

Change from baseline will only be calculated for patients with both baseline and post baseline values as:

$$\text{Change from baseline} = \text{postbaseline value} - \text{baseline value}.$$

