9.4.2. Primary Endpoints Analysis

AEs (deaths, SAEs, TEAEs, and hypoglycemia, including severe hypoglycemia)

Frequency and percentage of AE occurrence (including deaths, SAEs, TEAEs, hypoglycemia, including severe hypoglycemia and GI disorders) will be presented for the study duration using safety population.

The proportion of patients with AEs and SAEs occurring within the duration of the study (24 weeks) after being administered dulaglutide 1.5 or 0.75 mg will be presented.

The proportion of patients with AEs, TEAEs, and SAEs occurring within the duration of the study (24 weeks) after being administered dulaglutide 1.5 or 0.75 mg and 95% CIs will be estimated based on normal approximation.

The incidence of AE (death, SAE, and TEAE) will be summarized. The rate per year will be assessed using a negative binomial model with the log of the study treatment exposure time as an offset variable.

The incidence of hypoglycemic AEs will be summarized. The number of hypoglycemic events per subject over the study period will be analyzed as continuous variables and will be summarized (mean, median, SD, SE, minimum, and maximum).

The rate per year of hypoglycemic events, that is, the number of hypoglycemic events per patient-year (365.25 days) will be assessed using a negative binomial model, with baseline HbA1c and baseline insulin usage as covariates and the log of the study treatment exposure time as an offset variable.

The incidence of AEs will be calculated based on the number of new AEs out of the total eligible population using the following formula:

$$\text{Number of new AEs post intervention/Total eligible population *100.}$$

Exposure-adjusted AE incidence will be presented by the severity and preferred term for the primary analysis.

It is defined as

Number of patients with new or worsened AEs during treatment period

Patient-year exposure/365.25

Patient-year exposure is counted in days up to the AE (or end of time at risk for subjects without AE).

Incidence of gastrointestinal AEs

The incidence of GI AEs per week will be plotted over time from baseline up to 24 weeks. The proportion of subjects with at least 1 GI AE will be plotted from baseline up to Week 24. A plot of prevalence by severity (mild, moderate, or severe) for nausea, vomiting, and diarrhea over the 24-week period will be provided for the rate of GI AEs.

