6.2 Full Analysis Set (FAS)

All patients who received at least 1 dose of study treatment and have at least 1 measurement of HbA1c after study treatment.

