11.2 Analysis

Population: FAS

Stratification: Table: Add the strata as needed in case subjects with dose modification exceeding 20% based on enrolled population as per section 7.3:

- a. Subjects on 1.5 mg only
- b. Subjects on 0.75 mg only
- c. Subjects with any dose modification*

* Subjects who have received at least one dose of 1.5 mg and at least one dose of 0.75 mg

Listing: By subject

Statistics: Baseline and Demographic variables will be summarized and listed. Overall summaries will include descriptive statistics for continuous measures (number of patients, mean, SD, median, minimum, maximum, interquartile ranges, number of missing values) and for categorical measures (sample size, frequency, and percentages and number of missing values).

The listing will be presented for diabetes diagnosis data at screening. Summary of duration of type 2 diabetes and associated baseline treatment will be presented.

12. Exposure and Compliance to the treatment

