20.3.2 Analyses

Population: SAF and PP

Stratification: Table: Add the strata as needed in case subjects with dose modification exceeding 20% based on enrolled population:

- a. Subjects on 1.5 mg only
- b. Subjects on 0.75 mg only
- c. Subjects with any dose modification*

* Subjects who have received at least one dose of 1.5 mg and at least one dose of 0.75 mg

Statistics: The actual values and change from baseline will be summarized by descriptive statistics (n, missing values, mean, median, SD, SE, minimum, and maximum) by visit. No multiplicity adjustment will be done.

The analysis of Mean change in Systolic Blood Pressure (mmHg), Diastolic Blood Pressure (mmHg) and Pulse (beats per minute) at 24 weeks will use the MMRM. Missing data will be assumed missing at random and will be accommodated by the MMRM. The MMRM using restricted maximum likelihood will be done for analyses (note: statistical comparison will not be conducted)

during the entire study period. An unstructured covariance structure will be used to model the within-patient variability and implicitly adjust for missing data. If this analysis fails to converge, the following covariance structures will be tested in order.

1. Toeplitz with heterogeneity
2. Autoregressive with heterogeneity, by visit
3. Compound symmetry with heterogeneous variances, by visit
4. Toeplitz
5. Autoregressive
6. Compound symmetry without heterogeneous variances, by visit

The first covariance structure that converges will be used. The Kenward-Roger approximation will be used to estimate denominator degrees of freedom. Significance tests will be based on least-squares mean using Type III sum of squares.

If none of the models converge then an analysis of covariance using LOCF imputation with similar terms as in the MMRM (except no terms that include visit) will be used in its place. The model will evaluate the change from baseline in SBP, DBP and pulse rate respectively as the dependent variables and the baseline value of SBP, DBP and pulse rate respectively as covariate. Separate model will be run for each parameter.

The MMRM for each of the endpoints will include the respective baseline score and any covariate. Baseline HbA1c and baseline insulin use will be included as covariate in the model if convergence is met. If convergence is not met with baseline insulin level and insulin regimen as covariates, then just insulin use(yes/no) will be used for insulin usage.

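### SAP section 18 runs all three primary safety endpoints on FAS and PP, although the protocol assigns safety endpoints to the safety set

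*SAP*

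**What the plan says.** The current protocol assigns the population for safety in three places. Section 9.3 reserves the FAS for efficacy and says "the safety analysis set is used to analyze the endpoints and assessments related to safety". Section 9.4.1 adds that "safety analyses will be conducted on the safety population". Section 9.4.2, on the primary endpoints, says that AE frequencies and percentages, GI disorders included, "will be presented for the study duration using safety population". Section 9.4.5 asks for the AE analyses to be repeated on the per-protocol set.

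The SAP gives a different population for each primary endpoint. Sections 18.1.2 (incidence of AEs), 18.2.2 (proportion with AEs and SAEs) and 18.3.2 (GI AEs) each read "Population: FAS and PP". SAP 6.2 defines the FAS as "All patients who received at least 1 dose of study treatment and have at least 1 measurement of HbA1c after study treatment". The safety set (SAP 6.4) needs only one dose.

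Elsewhere the SAP keeps the safety set for safety data: the AE tables (15.2.1, 15.2.2), laboratory tests (16.2) and vital signs (17.2). Even the exploratory blood pressure and pulse endpoint in 20.3.2 has "Population: SAF and PP". SAP section 5 declares no change from the planned analyses.

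**The concern.** Entry to the primary safety analysis depends on an efficacy measurement taken after treatment starts. Under the Schedule of Activities, HbA1c after dosing is scheduled only at Weeks 12 and 24, and the Week 4 and Week 8 visits are telehealth. Protocol 4.2 says GI effects usually come early in therapy. A patient can therefore have the event of interest and leave the study before becoming eligible for the FAS.

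The PP set is a subset of the FAS, so it cannot recover such a patient. The following are specified only in section 18, and so would not exist on the safety set:

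- the 95% confidence intervals for the AE and SAE proportions;
- the negative binomial rates;
- the exposure-adjusted measure ("Exposure-adjusted AE incidence will be presented by the severity and preferred term for the primary analysis");
- the overall hypoglycemia analyses;
- the Cox models and Kaplan-Meier plots for nausea, vomiting and diarrhea.

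The report would also show the same events over two denominators, the safety set in section 15 and the FAS in section 18. Safety is the study's only primary objective, and the study is meant to satisfy a marketing-authorization condition.

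**Working it through.** **Who is in which set**

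| Treated patient | Safety set | FAS | PP |
|---|---|---|---|
| Has a post-dose HbA1c | in | in | in if the PP criteria are met |
| Dies, withdraws or is lost before any post-dose HbA1c | in | out | out |
| Stops dulaglutide but stays on visits (Protocol 7.1) and gives an HbA1c | in | in | depends on the PP criteria |

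An HbA1c taken at the early discontinuation visit, which Protocol 7.2 asks for where possible, also keeps a patient in the FAS.

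**The plan's own figures (Protocol 9.6).** 250 × 0.80 = 200 treated and 200 × 0.80 = 160 at the end, so both reproduce. That leaves 40 dropouts. No precision calculation is stated. The documents do not say how many patients would lack a post-dose HbA1c. I take e = 0 to 40 excluded; 10 to 30 corresponds to 25% to 75% of the dropouts leaving before any post-dose HbA1c.

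All other inputs below are assumptions for illustration.

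**1. Proportion with an event.** Let incidence in the FAS be 30% and risk in the excluded be q.

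Safety-set proportion = [e × q + (200 − e) × 0.30] / 200

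| e | q = 0% | 10% | 30% | 50% | 100% |
|---|---|---|---|---|---|
| 10 | 28.5% | 29.0% | 30.0% | 31.0% | 33.5% |
| 20 | 27.0% | 28.0% | 30.0% | 32.0% | 37.0% |
| 30 | 25.5% | 27.0% | 30.0% | 33.0% | 40.5% |
| 40 | 24.0% | 26.0% | 30.0% | 34.0% | 44.0% |

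Section 18 would report 30.0% in every cell. Equal risk gives no bias.

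**2. Exposure-adjusted incidence (formula in SAP 18.1.1).** Take 180 in the FAS: 54 with a first event at day 28, and 126 at risk to day 168.

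FAS person-time = (54 × 28 + 126 × 168) / 365.25 = 22,680 / 365.25 = 62.09 years

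FAS rate = 54 / 62.09 = 87.0 per 100 patient-years

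Add 20 excluded patients, k of them with an event at day 14 and the rest leaving at day 42.

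Safety-set rate = (54 + k) / {62.09 + [14k + 42(20 − k)] / 365.25}

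- k = 0: 54 / 64.39 = 83.9
- k = 6 (30%): 60 / 63.93 = 93.8
- k = 20: 74 / 62.86 = 117.7

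The two rates are equal at k of about 1.9 (9.4%). Varying the FAS event day from 14 to 42, the exit day from 28 to 70 and the excluded event day from 7 to 21 moves this to between 6.2% and 15.4%. Excluded patients contribute little time at risk. So, under these inputs, equal 30% risk does not protect this measure: the FAS gives 87.0 against 93.8.

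**3. Deaths.** Suppose 20 are excluded, two of them deaths before any post-dose HbA1c, with no other deaths. Section 18 shows 0/180 (exact 95% CI 0 to 2.0%); the safety set would show 2/200 = 1.0% (0.1% to 3.6%). These intervals are illustrative, because SAP 18.2.2 names the exact method for total AEs and SAEs only.

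**The case against.** The strongest reply is that little is lost. SAP 15.2 and its subsections give an overview of AEs and SAEs and tabulate TEAEs, SAEs, deaths and severity on the safety set as patients, events and percentages. SAP 18.3.1 treats every term coded as GI as a GI event for the safety analysis, so safety-set GI counts exist too. Severe hypoglycemia must be reported as an SAE (Protocol 8.3.5) and so appears in section 15. Exact limits for a proportion could be worked out by hand from those tables. All of this is right, and it means the events do not vanish. It does not supply the model-based rates, the exposure-adjusted incidence, the overall hypoglycemia analyses or the time-to-event results.

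Second, the safety-population wording in Protocol 9.4.2 is attached to the frequency-and-percentage sentence; the sentences on confidence intervals, rates and Cox models name no population. That is a fair reading. For those analyses the requirement comes from the general rules in 9.3 and 9.4.1, which cover all safety endpoints.

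Third, the number excluded may be zero, and Protocol 7.2 expects discontinuation to be uncommon. Both set sizes appear in the disposition table (SAP 10.1), exclusions are reviewed with reasons before lock (SAP section 6), and there is no hypothesis test on the primary endpoints. These points limit the likely damage and make it visible. They do not remove the conflict.

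The PP repeat is not an error, since Protocol 9.4.5 plans it. The SAP also cites protocol version 1.0, which was not available, so I do not say that SAP section 5 was untrue when written; it conflicts with the current protocol.

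**Conclusion.** The concern holds. All three primary safety endpoints are assigned to a population that the current protocol reserves for efficacy, and the SAP gives no reason. Any death before a post-dose HbA1c is certain to be missing from the section 18 numerators. For the death proportion and for other events, the bias may be downward, absent or upward, depending on how event risk in the excluded compares with risk in those retained.

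The size cannot be predicted from the documents. The calculations show what assumed inputs would do and are not forecasts. The correction is required because the rule is wrong as written for every primary endpoint, whatever the eventual number excluded.

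**What to change.** In SAP 18.1.2, 18.2.2 and 18.3.2, name SAF as the primary population with PP as supportive. Keep FAS for HbA1c, body weight and FBG. If FAS results for safety are still wanted, label them supplementary and declare them in SAP section 5.

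A useful but optional companion is a safety-set version of the baseline table in SAP 11.2, which now has "Population: FAS" only. It would describe age, sex and BMI for the population behind the primary results.

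The cost is three population lines, a population flag in the programs, and matching headers in the separate output templates, carried through the subgroup and any dose-stratum repeats, plus one table if the companion is adopted. No new data are needed. AE percentages and rates may move either way.

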9.6. Sample Size Determination

An estimated 250 participants will be screened, and assuming a 20% screen failure rate, an estimated 200 participants will be initiated on IP. Assuming a 20% dropout rate by the end of the study period, approximately 160 patients at the end of the study would allow for an adequate description of AEs and other safety outcomes. This is required to fulfill the market authorization clause.

10. Supporting Documentation and Operational Considerations

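### The planned model for the annual death rate has no finite solution at 0 or 1 death, and the SAP has no fallback that works at low counts

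*SAP*

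**What the plan says.** SAP 18.1.2 defines the rate per year as the "number of deaths, SAE, and TEAEs per subject per year over the study period" and assigns it to a negative binomial model with log exposure time as offset. It then says that "the model will be performed as per details mentioned below".

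Those details name covariates: "The Negative Binomial Model i.e., the generalized linear model will be used with baseline HbA1c and baseline insulin usage". Insulin enters as total daily dose and as regimen, with patients not on insulin given dose 0 and their own regimen level. The promised output is: "The incidence rate, least square mean and corresponding 95% confidence interval will be provided for table".

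There is one rule for estimation failure: "In case convergence is not met with the above variables, only baseline HbA1c and baseline insulin usage(Yes/No) will be considered". A second rule repeats the analysis without a covariate when more than 20% of its values are missing. That rule depends on missing data, not on event counts.

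The analysis runs in the FAS and the per-protocol set and is repeated in age, HbA1c, sex and BMI subgroups (eight levels).

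Protocol 9.4.2 is sparser: "The rate per year will be assessed using a negative binomial model", with log exposure as offset and no covariates for this rate. It names covariates only for the hypoglycemia rate.

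**The concern.** A log-link count model needs events at every level of a categorical covariate. If one insulin group has no events, its log rate tends to minus infinity and no maximum likelihood estimate exists. If there are no events at all, the intercept diverges too. The fallback drops dose and regimen but keeps insulin Yes/No, which is the term that fails when deaths are very few.

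The study documents safety for a marketing-authorization clause. With few or no deaths, the useful figure is an upper bound on the death rate, and the specified method cannot give one at the counts most likely to occur. Nor can the convergence trigger be relied on, because software may report convergence on a diverging coefficient and let a meaningless interval into the table.

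**Working it through.** **Plan's own figures.** Protocol 9.6 states: "An estimated 250 participants will be screened, and assuming a 20% screen failure rate, an estimated 200 participants will be initiated on IP". Check: 250 × (1 − 0.20) = 200. It continues: "Assuming a 20% dropout rate by the end of the study period, approximately 160 patients at the end of the study". Check: 200 × (1 − 0.20) = 160. Both reproduce.

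**Exposure (assumption: dropouts contribute half the period on average).** 160 + 40 × 0.5 = 180 patient-equivalents. 180 × 24 × 7 / 365.25 = 82.8 patient-years for all treated patients. The FAS would have somewhat less.

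**Likely number of deaths.** Neither document gives a death rate, so a range is assumed. With m = rate × 82.8, P(at most 1) = exp(−m) × (1 + m):

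| Assumed annual death rate | m | P(0 deaths) | P(0 or 1 death) |
|---|---|---|---|
| 0.2% | 0.17 | 85% | 99% |
| 0.5% | 0.41 | 66% | 93% |
| 1% | 0.83 | 44% | 80% |
| 2% | 1.66 | 19% | 51% |

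**Does a finite solution exist?** This was checked with a linear-programming separation test, 400 to 600 simulated datasets per setting, n = 200, events placed at random. At any fixed dispersion the condition is the same for negative binomial and Poisson. Assumptions: HbA1c mean 8.8 and SD 1.0 within 7.5 to 11.5; insulin use 20%, 30% or 50%; for the first-choice model, 70% no insulin, 20% basal and 10% premix.

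| Patients with an event | Fallback, insulin use 20% / 30% / 50% | First-choice model (HbA1c, dose, regimen) |
|---|---|---|
| 0 | 0% / 0% / 0% | none possible |
| 1 | 0% / 0% / 0% | 0% |
| 2 | 33% / 38% / 49% | 0% |
| 3 | 47% / 62% / 77% | 8% |
| 5 | 70% / 82% / 94% | 29% |
| 8 | 85% / 95% / 99% | 42% |
| 10 | 90% / 98% / 99.8% | 63% |

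Results for the fallback at n = 160 are nearly the same.

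**Analytic check of the fallback.** The chance that d events fall in both insulin groups is 1 − p^d − (1 − p)^d, with p the proportion on insulin. For p = 0.3: d = 1 gives 0, d = 2 gives 0.42, d = 3 gives 0.63. This agrees with the simulation.

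**Offset-only model (Protocol 9.4.2).** It fails at 0 deaths and has a finite rate from 1 death upward.

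**Convergence flag.** The fallback form was fitted to 200 simulated datasets with 1 death (30% on insulin, dispersion fixed at 0.01, Python statsmodels). The software reported convergence in roughly 87% to 90% of fits, always with a standard error above 50 for the insulin coefficient. SAS may behave differently.

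**Analysis sets and subgroups.** The per-protocol set requires completion of 24 weeks (SAP 6.3), so only a death during follow-up could count there. The FAS requires a post-treatment HbA1c (SAP 6.2), scheduled at Weeks 12 and 24, so it loses most early deaths. If 8 patients overall had an SAE (assumed), a subgroup holding 20% of patients would contain at most one of them with probability 0.8^8 + 8 × 0.2 × 0.8^7 = 0.50.

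**Exact Poisson alternative.** Limits are χ²(0.025; 2d)/2 and χ²(0.975; 2d + 2)/2, divided by 82.8 and expressed per 100 patient-years:

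- 0 deaths: 0 (0 to 4.5)
- 1 death: 1.2 (0.03 to 6.7)
- 2 deaths: 2.4 (0.3 to 8.7)
- 3 deaths: 3.6 (0.7 to 10.6)

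At 83.3 patient-years the bound for 0 deaths is 4.4, so the exposure assumption matters little.

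**The case against.** The strongest reply is that the safety results do not depend on this model. Frequencies and percentages of deaths and SAEs are planned. Exposure-adjusted incidence by severity is planned too, and the severity field includes death, so a crude exposure-based death figure will be available. SAP 18.2.2 gives Clopper-Pearson intervals for the proportions with AEs and SAEs, and a fatal event is an SAE. The protocol states no hypothesis. All of this stands, and it limits the harm to one modelled rate and its interval. It does not fill the gap for deaths: the Clopper-Pearson interval is stated for total AEs and SAEs, and no interval is stated for exposure-adjusted incidence.

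A reader might infer more than the documents support:

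- **That any handful of deaths defeats the plan.** Failure is certain only at 0 or 1. At 2 to 5 deaths the fallback is solvable in about 33% to 94% of datasets. Figures for the first-choice model alone ignore this.
- **That the SAE rate will not exist.** Neither document gives an SAE rate. At an assumed 8 to 10 patients with an SAE, the fallback is solvable in 85% to 99.8% of datasets.
- **That the protocol has the same defect.** It names only the offset; the covariates reach deaths through the SAP's cross-reference.
- **That one death per patient invalidates a negative binomial model.** The dispersion estimate would be expected at zero and the model becomes Poisson, which does not in itself remove the rate or CI.

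The SAP text could also be read as one combined event count, since separate models per outcome are not spelled out. On that reading the problem recedes, but no separate death rate would be produced.

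**Conclusion.** The point holds as a missing low-count rule for deaths. Read as separate models for deaths, SAEs and TEAEs, SAP 18.1.2 gives no finite death-rate estimate at 0 or 1 death, under either the first-choice model or the fallback. At 0 deaths the protocol's offset-only model fails as well. At 2 or 3 deaths the outcome is uncertain. Sparse SAEs, the subgroup repeats and the per-protocol set are at risk but not certain to fail.

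The result at 0 or 1 death follows from the model's form and needs no assumption. How likely those counts are depends on the assumed death rates and exposure. The percentages at 2 or more events depend on the assumed insulin use and HbA1c distribution. This should be corrected before database lock, but it does not threaten the descriptive safety tables.

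**What to change.** Amend SAP 18.1.2:

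- **Deaths:** report events per 100 patient-years with an exact Poisson 95% CI and no covariates.
- **SAEs:** keep the negative binomial model. If an insulin group has no events, or the event count is below a pre-stated minimum, drop the covariates and keep the exposure offset. With zero events, give the exact Poisson upper bound. Base the trigger on event counts, not on a convergence flag. Replacing the model by an exact Poisson interval for all SAEs would go too far: SAEs can recur within a patient, and such an interval could then be too narrow.
- **TEAEs:** no change.
- **Scope:** apply the same rules in the subgroups and the per-protocol set, and state that each outcome is analysed separately.

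The cost is a few SAP sentences and simpler programming. The death rate would be unadjusted, which loses little in a single-arm descriptive study.
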